	established to collect more detailed information of cancer staging, treatment and follow-up data from hospitals with more than 500 new cancer cases diagnosed annually. The number of recorded items increased from 20 to 65 in 2002, further to 95 in 2007, and to 114 in 2011. In 2003, Cancer Control Act was introduced with all reporting hospitals mandated to submit cancer patient information to the cancer registry. To ensure quality of cancer registries and enhancing the quality of cancer registry data, Taiwan Society of Cancer Registry was established in 2006, conducting random medical record review to ensure data accuracy since 2010. TCR data from 2000 through 2018 will be used for this study.		
Study size:	Based on the result of study by Wedzicha JA, et al, (where at least 25% of the patients in the Tio/Olo group have a first moderate or severe exacerbation at 127 days [95% CI, 107 to 149] and in ICS/LABA group at 87 days [95% CI, 81 to 103] (HR = 0.78, [95% CI 0.70 to 0.86])), we assume that at least 25% of patients in the ICS/LABA experienced a first moderate or severe COPD exacerbation at 103 days and the HR of Tio/Olo to LABA/ICS is 0.9. For a study duration of 6 years, a total of 4978 patients (2489 patients each arm) are needed to detect the difference between the two arms with 2-sided alpha of 0.05 and 90% power		
Data analysis:	All variables, including patient characteristics, baseline measures, and outcomes, will be analysed descriptively. All analyses will be presented for each exposure group (Tio+Olo vs LABA/ICS) overall. We will first describe formation of the study cohort. Patient characteristics at baseline in patients treated with Tio+Olo and patients treated with LABA/ICS will be described separately using standard descriptive statistics after propensity score matching. Absolute standardized differences (ASDs) will be used to compare the characteristics between the two groups after propensity score matching, in which a >0.1 ASD indicates a meaningful difference.		

NIS Protocol Page 17 of 48 BI Study Number: 1237-0110 c38660249-01

Name of same and			
Name of company: Boehringer Ingelheim	1		
Name of finished me			
product:	dicinal		
Spiolto Respimat			
Name of active ingre			
Tiotropium + Olodate	erol		
{R03AL06}			
Protocol date:	Study	Version/Revision:	Version/Revision date:
110totol unter	number:	V OI SIOII/ILO VISIOII	v er stom tte vision dave.
23 May 2022	1237-0110	1.0	NA
	annualized rate of exposed group re	ate of moderate or severe COPE of prescriptions of rescue medical elative to LABA/ICS group, alo derived using negative binomia	ations, ratio of Tio+Olo – ng with 95% confidence

NIS Protocol Page 18 of 48 BI Study Number: 1237-0110 c38660249-01

Name of company:			
Boehringer Ingelheim			
Name of finished medicinal product: Spiolto Respimat			
Name of active ingre Tiotropium + Olodate {R03AL06}			
Protocol date:	Study number:	Version/Revision:	Version/Revision date:
23 May 2022	1237-0110	1.0	NA
Milestones:	IRB/IEC approval: 22-Oct-2020 Feasibility assessment: 2020. Q3 EU PAS Registration: 01-Jun-2022 Full analysis: Data Access: 15-Jun-2022 Complete data analysis: 30-Aug-2022 Final report of study results: 15-Oct-2022 Publications timeline: Abstract: 2023 ATS.		

NIS Protocol Page 19 of 48 BI Study Number: 1237-0110 c38660249-01

Proprietary confidential information © 2022 Boehringer Ingelheim International GmbH or one or more of its affiliated

5. AMENDMENTS AND UPDATES

None

NIS Protocol Page 20 of 48 BI Study Number: 1237-0110 c38660249-01

Proprietary confidential information © 2022 Boehringer Ingelheim International GmbH or one or more of its affiliated

6. MILESTONES

Milestone	Planned Date
IRB/IEC approval	Oct 2020 (completed)
Feasibility assessment	Oct 2020 (completed)
EU PAS Registration	01/Jun/2022
Full analysis	
Data Access	15/Jun/2022
Complete data analysis	30/Aug/2022
Final report of study results	15/Oct/2022

NIS Protocol Page 21 of 48 BI Study Number: 1237-0110 c38660249-01

Proprietary confidential information © 2022 Boehringer Ingelheim International GmbH or one or more of its affiliated

7. RATIONALE AND BACKGROUND

COPD is a leading cause of morbidity and mortality throughout the world. Long-acting bronchodilator medications, which include long-acting β2-agonists (LABAs) and the long-acting muscarinic antagonists (LAMAs) such as tiotropium, are the central maintenance therapy to the management of COPD, with inhaled corticosteroids (ICSs) added with increasing severity. The up-to-date GOLD guideline recommends to initiate ICS/LABA in patients with high blood eosinophils level and frequent exacerbation history[P21-01394]. However, ICS containing therapy has been widely used inappropriately in real world practice.

The role of ICS in COPD has been debated for decades and studies have been conducted to investigate the effect of ICS-containing therapy in patients with COPD. INSPIRE [P07-11820] study indicated that ICS/LABA and tiotropium showed similar effects on the reduction of exacerbations, while the risk of pneumonia was higher in the ICS/LABA group. And the FLAME [P16-05628] study showed LAMA/LABA was superior to ICS/LABA in terms of exacerbation prevention, while in some newly published data focusing on FDC triple therapy showing reversed results.

With more and more fixed dose combination medications, i.e. LAMA/LABA, ICS/LABA/LAMA, approved and prescribed in recent years, it is of clinical interests to understand the effectiveness and safety profile of these therapies in real world settings.

The aim of this real world study is to assess effectiveness and safety profile between tiotropium/olodaterol (Tio/Olo) and ICS/LABA. The primary outcome of the study will be time to first moderate or severe COPD exacerbations. Other outcomes include time to ICS/LABA/LAMA escalation, rate of escalation to triple therapy, pneumonia and rescue medication use.

NIS Protocol Page 22 of 48 BI Study Number: 1237-0110 c38660249-01

Proprietary confidential information © 2022 Boehringer Ingelheim International GmbH or one or more of its affiliated

8. RESEARCH QUESTION AND OBJECTIVES

Primary objective:

• To compare time to the first moderate or severe COPD exacerbations between initiators of Tio/Olo and ICS/LABA in a real world setting;

Secondary objectives:

- To compare time to escalation to triple therapy between initiators of Tio/Olo and ICS/LABA;
- To compare the rate of escalation to triple therapy between initiators of Tio/Olo and ICS/LABA;
- To compare the time to first hospitalization for community-acquired pneumonia between initiators of Tio/Olo and ICS/LABA;
- To compare the number of prescriptions of rescue medication between initiators of Tio/Olo and ICS/LABA;
- To compare the annualized rate of moderate or severe COPD exacerbation between initiators of Tio/Olo and ICS/LABA..

NIS Protocol Page 23 of 48 BI Study Number: 1237-0110 c38660249-01

Proprietary confidential information © 2022 Boehringer Ingelheim International GmbH or one or more of its affiliated

9. RESEARCH METHODS

9.1 STUDY DESIGN

This study will be a non-interventional cohort study based on existing data (NISed).

The aim of this real world study is to assess effectiveness and safety profile between tiotropium/olodaterol (Tio/Olo) and ICS/LABA. The primary outcome of the study will be time to the first moderate or severe COPD exacerbations. Other outcomes include time to ICS/LABA/LAMA escalation, rate of escalation to triple therapy, pneumonia and rescue medication use.

9.2 SETTING

9.2.1 Study sites

Data used in this study will come from the Taiwan National Health Insurance (NHI) claims data between 2014 and 2019.

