9.2.2 Study population

Inclusion criteria:

- At least oneprescriptions for Tio/Olo combined inhaler or a LABA/ICS combined inhaler between 1st January 2014 and 31st December 2019.
 - a) The first dispensing of either Tio/Olo or LABA/ICS combined inhaler will be defined as the index date;
 - b) For the main analyses, only fixed dose combination (FDC) inhalers will be included.
- 2. Aged \geq 40 years on the index date
- 3. At least one diagnosis of COPD at any time prior to or on the index date;
- At least one year of continuous medical and health insurance plan prior to the index date will be required to allow for a look-back period for the covariates and identification of new use of the study drugs;
- 5. At least one record in the health insurance system database;

Exclusion criteria:

- 1. Any use of Tio/Olo, ICS/LABA, or ICS/LAMA/LABA in free or fixed form for one year prior to the index date;
- Individuals with asthma, allergic rhinitis, lung cancer, interstitial lung disease, or lung transplant identified at any time prior to the index date

NIS Protocol Page 24 of 48 BI Study Number: 1237-0110 c38660249-01

Proprietary confidential information © 2022 Boehringer Ingelheim International GmbH or one or more of its affiliated

For the analysis of the primary outcome, individuals will be followed up from the index date until the earliest of the date of: the follows, whichever first 1) moderate or severe COPD exacerbation; 2) disenrollment; 3) the end of the study period; 4) death; 5) discontinuation of the index drug use as a lapse of 1.5 months without subsequent prescription (except for switching from the index ICS/LABA to a different ICS/LABA); 6) adding ICS mono on top of Tio/Olo, or adding LAMA momo on top of the index ICS/LABA

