9.3.3 Covariates

Demographic characteristics and cohort entry information:

Sex

NIS Protocol Page 26 of 48 BI Study Number: 1237-0110 c38660249-01

Proprietary confidential information © 2022 Boehringer Ingelheim International GmbH or one or more of its affiliated

- Age
- Calendar year of cohort entry
- Season of index date (winter, spring, summer, fall)

Additional, the following clinical characteristics will be measured during the 1 year pre-index baseline period:

Previous COPD treatments

- ➤ LAMA monotherapy
- ➤ LABA monotherapy
- > ICS monotherapy
- ➤ LAMA/ICS combination therapy

Use of other respiratory drugs

- Mucolytics
- > Theophylline
- ➤ Short-acting beta-agonists
- > Short-acting muscarinic antagonists
- Previous acute COPD exacerbation (measured both 12 months and in the 30 days prior to cohort entry), categorized as 0, 1 or 2+.
 - ➤ All exacerbations (Moderate+Severe)
 - An outpatient visit with a diagnosis code for COPD in any field + a prescription for an oral corticosteroid or an antibiotic for respiratory infections (Moderate)
 - ➤ Hospitalizations or emergency room visits with a primary diagnosis for COPD (Severe)
- Hospitalizations caused by exacerbation of COPD in 12 months prior to the index date:
 - **>** 0;
 - **>** 1;
 - **>** 2+;
- all-cause hospitalizations in 12 months prior to index date:
 - > 0;
 - **>** 1;
 - **>** 2+;
- Comorbidities:
 - > Cardiovascular disease
 - > Cerebrovascular disease
 - Diabetes
 - > Chronic kidney disease
 - > Pneumonia
 - > Cancer
 - Cirrhosis

NIS Protocol Page 27 of 48 BI Study Number: 1237-0110 c38660249-01

Proprietary confidential information © 2022 Boehringer Ingelheim International GmbH or one or more of its affiliated

- Charlson Comorbidity Index (CCI)
- History of medications dispensed in the 12 months before or on the index date will be identified from the pharmacy dispensing history:
 - > Cardiovascular drugs:

Antihypertensives

Antiarrhythmics

Nitrates

heart failure medications

- ➤ Lipid-lowering medications
- ➤ Blood glucose-lowering medications
- ➤ Anticoagulants and antiplatelet agents
- > Antibiotics
- ➤ Antineoplastic agents

COPD severity

The definition of the severity of COPD in this study was developed based on the information in previous studies, GOLD recommendations and clinical practice in Taiwan, see below. Patients who fulfil criteria for more than one category will be classified as being in the most severe category.

Criteria of COPD severity:

➤ Mild:

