## **6.2 SETTING**

Incident Tio/Olo combined inhaler or a ICS/LABA combined inhaler use would be identified from the Taiwan National Health Insurance (NHI) claims data through 2014 to 2019, with a 1-year look-back period to define new user.

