## ANNEX 1. ADDITIONAL INFORMATION

Table 1. Baseline characteristic of the study cohort

	Before propensity score match				After propensity score match			
	Tio/Olo cohort		ICS/LABA cohort		Tio/Olo cohort		ICS/LABA cohort	
	N	%	N	%	ASD	N	%	ASD
Gender								
Male								
Female								
Age								
40~54								
55~69								
70~84								
85+								
Calendar year of cohort entry								
2014								
2015								
2016								
2017								
2018								
2019								
Season of index date								
Spring (Mar-May)								
Summer (Jun-Aug)								
Fall (Sep-Nov)								
Winter (Dec-Feb)								
COPD treatments in 1 year prior to index date								
LAMA								
LABA								
ICS								
ICS+LAMA free combination								
Use of other respiratory drugs in 1 year prior to index date								
Mucolytics								
Theophylline								
Short-acting beta-agonists (SABA)								
Short-acting muscarinic antagonists (SAMA)								

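### The stated NHI claims window (2014–2019) opens on the same day as cohort entry, so it does not cover the full one-year look-back for any 2014 index date

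*Protocol*

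**What the plan says.** **Claims window.** Protocol 9.2.1 states: "Data used in this study will come from the Taiwan National Health Insurance (NHI) claims data between 2014 and 2019". The abstract and 9.4 say the same. SAP section 8 lists the data sources without years.

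**Entry window.** Inclusion 1 (Protocol 9.2.2) takes a study inhaler prescription "between 1st January 2014 and 31st December 2019", and "The first dispensing of either Tio/Olo or LABA/ICS combined inhaler will be defined as the index date". The Table 1 shell in SAP Annex 1 has 2014 as the first row under "Calendar year of cohort entry", so 2014 entrants are intended.

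**What needs the preceding year.**
- Washout, exclusion 1: no use of the listed combinations "in free or fixed form for one year prior to the index date".
- Covariates, Protocol 9.3.3: "clinical characteristics will be measured during the 1 year pre-index baseline period". These include earlier COPD drugs, exacerbations and hospitalizations.
- COPD severity (Protocol 9.3.3, SAP 7.3): based on dispensings and events in the 12 months before index.
- Inclusion 4: "At least one year of continuous medical and health insurance plan prior to the index date will be required".

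**Look-back in the SAP.** SAP 6.2 identifies incident use from "claims data through 2014 to 2019, with a 1-year look-back period to define new user". It gives no start date for the look-back data.

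**Other sources.** Protocol 9.4 does give earlier start years elsewhere: 2012 for the death files and 2000 for the cancer registry.

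**The concern.** Claims are the only named source of dispensings and visits. If they begin on 1 January 2014, the year before a 2014 index date lies partly or wholly outside the data.

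Two things would follow if 2013 claims are not extracted and 2014 entrants are kept. First, a patient already on ICS/LABA in 2013 could pass the washout at the first dispensing seen in 2014 and be treated as an initiator. Second, baseline history would be under-counted. SAP 9.2 treats claims as having no missing values, so unobserved history would read as no history. A patient with no visible treatment or events falls into the mild severity class, because that class includes treatment-naïve patients. These variables feed the propensity score, which uses every covariate except season (SAP 10.1).

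The criteria that apply at any time before index are cut short in the same way: the COPD diagnosis and the exclusions for asthma and other conditions. Protocol 9.9 says that patients with concomitant asthma may differ in disease course, treatment and response, so a missed asthma history is not harmless.

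**Working it through.** The plan gives no look-back figure of its own to reproduce. The check is date arithmetic, followed by the power effect of a later start.

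**1. Observable look-back.** Inputs: first claims date 1 January 2014 (Protocol 9.2.1, read literally), first index date 1 January 2014 (9.2.2), required look-back one year. Formula: days observed = index date minus 1 January 2014, capped at 365.

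| Index date | Days observed | Days required |
|---|---|---|
| 1 Jan 2014 | 0 | 365 |
| 1 Jul 2014 | 181 | 365 |
| 31 Dec 2014 | 364 | 365 |
| 1 Jan 2015 | 365 | 365 |

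No 2014 index date has a complete year. If entry were uniform over 2014 (an assumption), the mean would be (0 + 364)/2 = 182 days. If continuing users were indexed at their first 2014 refill, entry would be front-loaded and the mean lower.

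**2. Share of the entry window.** 1 January 2014 to 31 December 2019 is 2191 days, and 2014 is 365 of them: 365/2191 = 16.7%. This is a share of calendar time. The share of patients is not given.

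**3. Does inclusion 4 close the gap?** It asks for a year of insurance cover, not a year of extracted claims. With coverage above 99% (Protocol 9.4), nearly everyone would meet it. If it were read as a year of observed claims, it would remove every 2014 entrant and contradict inclusion 1 and Table 1. Both readings leave something to reconcile.

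**4. Can the bias be sized?** Let a fraction c of matched comparators be continuing users whose hazard is h times that of true initiators. A true HR of 0.90 (the planning value in Protocol 9.5) would then read as approximately 0.90/((1 − c) + c·h). The result is above 0.90 if h is below 1, and below 0.90 if h is above 1. The documents give neither c nor h, so neither size nor direction follows.

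**5. Power if entry starts in 2015.** Inputs from Protocol 9.5: HR 0.9, two-sided alpha 0.05, power 90%, N = 4978.
- Events for 90% power (Schoenfeld): 4 × (1.960 + 1.282)² / (ln 0.9)² = 3787 after rounding up.
- Implied event share, if 4978 patients yield exactly these events: 3787/4978 = 76%.
- If one sixth of patients were lost (assumption): N = 4978 × 5/6 ≈ 4148 and events = 3787 × 5/6 ≈ 3156. Power = Φ(√3156/2 × 0.1054 − 1.960) = Φ(1.00) ≈ 84%.
- If 4978 patients were still found, with uniform entry over five years, exponential event times (25% at 103 days) and no dropout (all assumptions): event share 79.5%, about 3957 events, power about 91%.

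Both power figures depend on the assumed event share. On-treatment censoring could lower it.

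**The case against.** The strongest reply is that the plan already intends a 2013 look-back and only the wording is loose. SAP 6.2 can naturally be read with 2014–2019 as the identification window and the look-back year added in front. Protocol 9.7 defers analytic detail to the SEAP, inclusion 4 exists expressly to allow a look-back, and the any-time-prior diagnoses presuppose older records. The 2014 row in Table 1 fits a planned 2013 look-back as well as it fits an oversight. This reading is plausible, and it stands as a possibility. But no section names 2013 claims or an extract start date, and Protocol 9.4 does give earlier years for the other two sources. Two analysts could build different cohorts from this text.

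A second reply concerns matching, and it also stands. Calendar year of entry is in the propensity score, the caliper is 0.06 SD of the logit, and outcomes are analysed only in matched patients (SAP 10.1). SAP 9.3 refers to years when Tio/Olo was not covered, without naming them. If 2014 was one of them and year enters as categories, few 2014 ICS/LABA patients would be matched and the primary hazard ratio would hardly move.

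A reader might infer more: that the look-back is wholly unobservable for 2014 entrants, that continuing users will be counted as new, or that the HR will be biased by a stated amount. The documents do not support these. The look-back is truncated, and is zero only on 1 January 2014. Misclassification depends on 2013 claims not being extracted and 2014 entrants being kept. Any numeric bias needs a treatment duration, a matched share and a relative hazard, none of which is given.

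**Conclusion.** The point holds as a conflict between the stated data window and the plan's own look-back rules. Read literally, the claims window leaves every 2014 index date short of the required year, by between 1 and 365 days. 2014 is 16.7% of the entry window by calendar time.

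The consequence is conditional. If 2013 claims are already in the extract, the defect is one of wording only. If they are not and 2014 entrants stay in, the new-user restriction and the propensity score inputs are weakened for those entrants. The effect on the hazard ratio has unknown size and sign, and may be small after matching. It should be resolved before the cohort is built, because the remedy is simple and the present text does not determine who is eligible.

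**What to change.** State in the Protocol abstract, 9.2.1 and 9.4, and in SAP 6.2, that NHI claims from 1 January 2013 to 31 December 2019 are used, with data before 2014 for look-back only. An earlier start would serve the any-time-prior diagnoses better; whichever date is chosen, say how far back those criteria reach. If 2013 claims are already planned, the cost is a sentence in each place. Otherwise it is at least one more year in the data request.

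If earlier claims cannot be obtained, set the first index date to 1 January 2015. Then:
- amend the dated objectives (Protocol abstract, SAP 5), inclusion 1 in both documents, the outcome time frames in Protocol 9.3.2 and the six-year duration in 9.5;
- remove the 2014 row from Table 1;
- state that the any-time-prior criteria are limited to claims from 2014;
- restate the power if patient numbers fall, with the assumed event share: about 84% if one sixth of the 4978 were lost, about 91% if 4978 are still found, on the assumptions shown above.

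The cost of this route is the loss of 2014 entrants. That loss may be slight in the matched cohort if Tio/Olo was not covered in 2014.

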9.2.2 Study population

Inclusion criteria:

- At least oneprescriptions for Tio/Olo combined inhaler or a LABA/ICS combined inhaler between 1st January 2014 and 31st December 2019.
 - a) The first dispensing of either Tio/Olo or LABA/ICS combined inhaler will be defined as the index date;
 - b) For the main analyses, only fixed dose combination (FDC) inhalers will be included.
- 2. Aged \geq 40 years on the index date
- 3. At least one diagnosis of COPD at any time prior to or on the index date;
- At least one year of continuous medical and health insurance plan prior to the index date will be required to allow for a look-back period for the covariates and identification of new use of the study drugs;
- 5. At least one record in the health insurance system database;

Exclusion criteria:

- 1. Any use of Tio/Olo, ICS/LABA, or ICS/LAMA/LABA in free or fixed form for one year prior to the index date;
- Individuals with asthma, allergic rhinitis, lung cancer, interstitial lung disease, or lung transplant identified at any time prior to the index date

NIS Protocol Page 24 of 48 BI Study Number: 1237-0110 c38660249-01

Proprietary confidential information © 2022 Boehringer Ingelheim International GmbH or one or more of its affiliated

For the analysis of the primary outcome, individuals will be followed up from the index date until the earliest of the date of: the follows, whichever first 1) moderate or severe COPD exacerbation; 2) disenrollment; 3) the end of the study period; 4) death; 5) discontinuation of the index drug use as a lapse of 1.5 months without subsequent prescription (except for switching from the index ICS/LABA to a different ICS/LABA); 6) adding ICS mono on top of Tio/Olo, or adding LAMA momo on top of the index ICS/LABA

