9.9 LIMITATIONS OF THE RESEARCH METHODS

Some important potential confounders are not available in the Taiwan NHI dataset. For example, pulmonary function data and duration of COPD may not be available in the data set. These variables will not be calculated so there might be confounding bias in the study. The definition for COPD severity was developed based on the previous evidence, treatment guideline and the clinical practice in Taiwan to reduce the bias.

COPD patients concomitant with asthma may be different from COPD patients without asthma in terms of the disease natural course, treatment regimen, and response to drugs. Therefore, COPD patients concomitant with asthma will be excluded from the primary analysis. Previous studies suggested that there might be misdiagnosis between COPD and asthma. To further exclude potential asthma patients,

In a database study like this, we can only rely on the available information to define outcomes, exposure and covariates. There will be misclassification of study variables. In the analyses, whenever possible, validated algorithm will be used to reduce misclassifications.

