## **6.3 STUDY POPULATION**

### **Inclusion Criteria:**

1. At least one prescription for Tio/Olo combined inhaler or a LABA/ICS combined inhaler between 1st January 2014 and 31st December 2019.
  - a) The first dispensing of either Tio/Olo or LABA/ICS combined inhaler will be defined as the index date;
  - b) For the main analyses, only fixed dose combination (FDC) inhalers will be included.
2. Aged  $\geq$  40 years on the index date
3. At least one diagnosis of COPD (ICD9: 491.x, 492.x, 496; ICD10: J41.x, J42, J43.x, J44.x) at any time prior to or on the index date;

[figure not shown]
4. At least one year of continuous medical and health insurance plan prior to the index date will be required to allow for a look-back period for the covariates and identification of new use of the study drugs;
5. At least one record in the health insurance system database.

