**Exclusion Criteria:**

1. Any use of LAMA/LABA, ICS/LABA, or ICS/LAMA/LABA in free or fixed form for one year prior to the index date (the free combination will be defined as the prescriptions of the interest products within 30 days of each other);
2. Individuals with asthma, allergic rhinitis, lung cancer, interstitial lung disease, or lung transplant identified at any time prior to the index date [REDACTED]; [REDACTED];

Relevant ICD codes and procedure code are provided in the Annex.

Figure 1. Patient selection flow chart

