### 7.3 COVARIATES

Demographic characteristics and cohort entry information:

- Sex
- Age
- Calendar year of cohort entry
- Season of index date (winter, Dec-Feb; spring, Mar-May; summer, Jun-Aug; fall, Sep-Nov )

Additional characteristics will be defined during the 1-year pre-index baseline period:

- Previous COPD treatments
  - LAMA monotherapy
  - LABA monotherapy
  - ICS monotherapy
  - LAMA/ICS free combination therapy
- Use of other respiratory drugs
  - Mucolytics
  - Theophylline
  - Short-acting beta-agonists
  - Short-acting muscarinic antagonists
- Previous acute COPD exacerbation (measured both 12 months and in the 30 days prior to cohort entry), categorized as 0, 1, or 2+.
  - All exacerbations (Moderate+Severe)
  - An outpatient visit with a diagnosis code for COPD in any field + a prescription for an oral corticosteroid or an antibiotic for respiratory infections (Moderate); prescriptions within 30 days of each other were considered as continuation of the initial exacerbation.
  - Hospitalizations or emergency room visits with a primary diagnosis for COPD

(Severe); hospitalizations or emergency room visits within 30 days of each other were considered as continuation of the initial exacerbation.

- Hospitalizations caused by exacerbation of heart failure in 12 months prior to index date, categorized as
  - 0;
  - 1;
  - 2+.
- All-cause hospitalizations in 12 months prior to index date;
  - 0;
  - 1;
  - 2+.
- Comorbidities:
  - Cardiovascular disease
  - Cerebrovascular disease
  - Diabetes
  - Chronic kidney disease
  - Pneumonia
  - Cancer
  - Cirrhosis
- Charlson Comorbidity Index (CCI)
- History of medications dispensed in the 12 months before or on the index date will be identified from the pharmacy dispensing history:
  - Cardiovascular drugs:
    - antihypertensives;
    - antiarrhythmics;
    - nitrates;
    - heart failure medications
  - Lipid-lowering medications
  - Blood glucose-lowering medications
  - Anticoagulants and antiplatelet agents
  - Antibiotics
  - Antineoplastic agents
- COPD severity

The definition of the severity of COPD in this study was developed based on the information in previous studies, GOLD recommendations and clinical practice in Taiwan, see below. Patients who fulfil criteria for more than one category will be classified as being in the most severe category.

Operational definition of COPD severity:

- Mild:

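### Asthma excludes a patient only if coded before the index date, while COPD may be coded on it, so asthma first recorded on the dispensing day stays in the cohort

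*Protocol*

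**What the plan says.** The index date is a dispensing day. Protocol 9.2.2 states: "The first dispensing of either Tio/Olo or LABA/ICS combined inhaler will be defined as the index date".

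Two diagnosis windows are set around that day:

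- **Inclusion 3 (COPD).** Protocol 9.2.2: "At least one diagnosis of COPD at any time prior to or on the index date". SAP 6.3 has the same window: "at any time prior to or on the index date". The index day counts.
- **Exclusion 2 (asthma and four other conditions).** Protocol 9.2.2: "Individuals with asthma, allergic rhinitis, lung cancer, interstitial lung disease, or lung transplant identified at any time prior to the index date". SAP 6.3 ends the same way: "lung transplant identified at any time prior to the index date". The index day is not mentioned. Redacted text follows in the SAP.

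Protocol 9.9 gives the purpose. It says that patients with both diseases may differ in disease course, treatment and response, and that "COPD patients concomitant with asthma will be excluded from the primary analysis". It adds: "Previous studies suggested that there might be misdiagnosis between COPD and asthma". The sentence after that, on excluding further possible asthma patients, breaks off in the public text.

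SAP 10.1 builds the propensity score from all covariates in SAP 7.3 except season. Asthma is not among them, and it has no row in the Table 1 shell.

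**The concern.** The index day is the day the treatment choice takes effect. An asthma code carrying that date may be the reason an inhaler containing a corticosteroid was chosen, and only one arm contains a corticosteroid. That would be confounding by indication, and excluding asthma is meant to prevent it.

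Nothing visible in the main analysis would correct it:

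- Matching cannot balance asthma directly, because asthma is not in the score.
- The rule in SAP 10.1 for adjusting covariates with a standardized difference above 0.1 covers only listed covariates.
- A later asthma code is not a censoring event.
- In SAP 7.2.1 a moderate exacerbation needs a COPD code in any field plus an oral corticosteroid or a respiratory antibiotic. An asthma attack in a patient coded for both diseases could therefore count as a primary event.

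The protocol describes the claims data as running from 2014 to 2019. If little earlier history is searched, asthma known for years could first appear in the data on the index day of an early entrant.

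**Working it through.** **Step 1: apply the two windows to one patient.** Take a patient aged 40 or over who meets the other criteria, with a COPD code on or before the dispensing day and a first asthma code on that day.

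| Criterion | Window as written | Result |
|---|---|---|
| Inclusion 3, COPD | before or on the index date | met |
| Exclusion 2, asthma | before the index date | not triggered |

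The patient enters. An asthma code dated even one day earlier would exclude the same patient. A patient with an asthma code and no COPD code fails inclusion 3 and cannot enter by this route. The same holds for allergic rhinitis, lung cancer, interstitial lung disease and lung transplant first recorded on the index day.

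**Step 2: what this could do to the hazard ratio.** The plan states no figure on this point, so there is none to reproduce. The following is an illustration.

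Inputs:

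- True hazard ratio 0.90, the planning value in Protocol 9.5.
- c, the share of the ICS/LABA arm with a first asthma code on the index day. Not in the documents; assumed 3% to 15%.
- h, the exacerbation hazard of those patients relative to the rest of their arm. Not in the documents; assumed 0.5, 0.7 and 1.5.
- Share in the Tio/Olo arm: set to zero at first.

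Treating the average hazard of the arm as its hazard throughout, which is a simplification:

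observed HR = 0.90 / [(1 − c) + c·h]

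| c | h = 0.5 | h = 0.7 | h = 1.5 |
|---|---|---|---|
| 3% | 0.90/0.985 = 0.914 | 0.90/0.991 = 0.908 | 0.90/1.015 = 0.887 |
| 15% | 0.90/0.925 = 0.973 | 0.90/0.955 = 0.942 | 0.90/1.075 = 0.837 |

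**Step 3: let the gap act in both arms.** With shares cT (Tio/Olo) and cI (ICS/LABA) and the same h in both:

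observed HR = 0.90 × [(1 − cT) + cT·h] / [(1 − cI) + cI·h]

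- Equal shares: the brackets cancel and the ratio stays at 0.90.
- cT = 3%, cI = 15%, h = 0.5: 0.90 × 0.985/0.925 = 0.958.
- cT = 3%, cI = 15%, h = 1.5: 0.90 × 1.015/1.075 = 0.850.

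On these assumptions, only a difference in shares between the arms produces bias, and its sign depends on h.

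**The case against.** **The wording may be loose rather than deliberate.** SAP 7.3 defines medication history as "History of medications dispensed in the 12 months before or on the index date", yet the Table 1 shell heads the same variable with a one-year window before the index date and leaves out the index day. So the SAP at least once omits the index day from a label for a window that includes it, and exclusion 2 may be meant the same way. This stands as a doubt about intent. It does not settle how a programmer should code the rule, and the written criterion still admits the patient in step 1.

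**There may be more on asthma than can be seen.** Redactions sit directly after exclusion 2 in the SAP, the sentence in Protocol 9.9 breaks off, the public protocol goes from 9.7.1 to 9.7.3, and an entry between 10.1 and 10.3 is redacted in the SAP contents. This stands. A reader might infer that the plan has no other safeguard, or that the redacted SAP text cannot matter because the protocol gives the criterion in full. The documents support neither inference.

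**The affected group is narrow.** It needs a COPD code, no earlier asthma or allergic rhinitis code, and a first asthma code on one particular day. This also stands. A reader might infer that the comparison turns partly into COPD against asthma. It does not: every patient has a COPD code, so the issue is COPD with an asthma code alongside it.

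**The one-sided leak is assumed.** The rule is the same for both arms and no count is given. That is correct, and step 3 shows how patients in the Tio/Olo arm would offset the bias.

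**The fix closes only one day.** Asthma first coded a week later still passes. True, but excluding on later codes would use information from after treatment start, whereas the index-day code is available at entry.

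**Conclusion.** As visibly written in both documents, the exclusion window is narrower than the inclusion window by exactly the day on which treatment starts, and it does not fully achieve the exclusion announced in Protocol 9.9. That follows from the text alone.

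Concentration in the ICS/LABA arm is a reasonable inference and not a documented fact. The size and direction of any bias are unknown. With assumed shares of 3-15% in ICS/LABA only and relative hazards of 0.5 to 1.5, a hazard ratio of 0.90 would read about 0.84 to 0.97. At a 3% share it moves only to about 0.89 to 0.91. A reader might take these ranges as evidence that the result will be biased towards or away from Tio/Olo; they rest on unsourced assumptions and show only that a modest imbalance could matter beside a planned reduction of 10%.

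The point is worth correcting because the remedy is simple, uses only information available at entry, and removes a plausible source of confounding by indication. Unseen asthma measures may reduce its importance.

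**What to change.** Extend exclusion 2 in Protocol 9.2.2 and SAP 6.3 to codes recorded before *or on* the index date, as in inclusion 3. This adds two words to each document and covers all five listed conditions. If index-day codes were already meant to count, the edit makes that explicit; if the difference was intended, state the reason.

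In the patient selection flow chart (SAP Figure 1), report by arm how many patients the index-day codes remove, with asthma shown separately. That replaces the assumed shares above with real counts.

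The cost is a slightly smaller pool for matching. The exclusion comes before matching, so removed patients may be replaced by others; the documents give no pool size. As a pessimistic case, take the planned 2489 pairs as giving 90% power, which needs 4(1.960 + 1.282)²/(ln 0.90)² ≈ 3787 events, and suppose that lost pairs are not replaced. A 5% loss leaves 2365 pairs and about 3787 × 2365/2489 = 3598 events. Power is then Φ(½√3598 × 0.1054 − 1.960) ≈ 88.5%. A 10% loss leaves 2240 pairs and about 86.8%.

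Asthma first coded after the index date remains as misclassification, a limitation that Protocol 9.9 already acknowledges.
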